5.2.3 Schedule

Details of the exact dose and time of administration of medication (day/month/year, h: min) will be documented in a specific patient's diary (Appendix VII; section 16.7) and reported in the case report form.

- Study medication: OTX015/MK-8628. All patients enrolled should receive first study treatment intake within 7 days after registration.
- The study treatment may be delivered to hospitalized patients or outpatients, depending of their need of supportive care according to investigator's judgment. However, for the once-a-day schedule, 3 patients by dose level (among a minimum number of patients of 6 by DL: 3

with AL and 3 with other malignancies) will be hospitalized at least 24 hours for complete PK sampling (see section 7.3.3.1) All other patients enrolled in the same DL will have limited PK sampling and will stay at least 8 hours at the hospital on day 1. For the BID schedule, all patients will be hospitalized for 24 hours for PK sampling.

- Route: Oral capsules will be swallowed with water in a fasted state before lunch, at least 3 hours after breakfast end), except the first dose (C1D1) that will be taken at the hospital before breakfast.
- Capsules must not be open or chewed.
 - Schedule: The schedule of administration will initially depend on the indication:
 patients with acute leukemia will initially take OTX015/MK-8628, over 14
 consecutive days followed by a 7-day rest period. Upon SMC decision, patients with acute leukemia will take OTX015/MK-8628 continuously without planned rest period, like patients with other haematological malignancies.

- patients with other malignancies will take OTX015/MK-8628 continuously without planned rest period

- In all cases, one cycle = 21 days by convention and day 22 = day 1 of next cycle.

ACUTE LEUKEMIA (initial schedule before amendment # 4)

4 5 6 7 8 9 10 11 12 13 14 15 19 20 21 3 16 17 18 22 etc

OTHER HEMATOLOGICAL MALIGNANCIES and ACUTE LEUKEMIA after amendment # 4

3 4 5 8 9 13 19 2 6 10 12 14 15 16 18 20 21 22 etc.

- Interruptions are planned in case of toxicity according to specific guide lines (see section 0). If study medication interruptions due to toxicity are regularly observed, the SMC may decide to modify the schedule and to assess new cohorts of patients with this modified schedule.

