# **12.2 TREATMENT EXPOSURE**

OTX015/MK-8628 treatment will be described by DL and overall.

The intended dose (mg, mg/kg, mg/m^2), study duration (days), treatment duration (days), number cycles initiated, cumulative dose (mg), absolute dose intensity (mg/week), the relative dose intensity (%).

In addition, treatment modifications will be described including, the number (%) of patients having at least one dose reduction (compared to the initial DL), intra-cycle interruption (dose 0 between two non 0 doses),

delay (definition), or dose increase (compared to the initial DL). The number of modifications per patient and per modification type will be reported and listings will be provided.

- Intended dose (mg,  $mg/m^2$ , mg/kg) = nb of planned courses \* planned dose by course
- Study duration =[(last cycle dose date first cycle dose date)/7 + 1]
- N days treatment intake (observed) =
- Actual cumulative dose (mg) = sum of all doses received from first cycle 1 day 1 to actual last day of treatment during the last cycle
- Absolute dose intensity (mg/week) = Actual cumulative dose / Actual duration
- Relative dose intensity (%)=[Actual dose intensity / Planned dose intensity]\*100
- Cumulative dose during the cycle 1  $(mg/m^2)$  = sum of all doses received during cycle 1 with
- Planned period of administration = 21 days

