# ii. **Exposure**

# Table ii-1 Extent of exposure, AL / OHM safety population

Intended dose*
Median (range) (mg/kg)
Median (range) (mg/m  )
Study duration (treatment
start to last dose last cycle
in days)
Median/patient (range)
Total
N days treatment intake
(observed)
Median/patient (range)
Total
N cycles started
Median/patient (range)
1
2
3
Cumulative dose
(observed)
Median (range) (mg/kg)
Median (range) (mg/m  )
Absolute dose intensity
(mg/week)
Median (range)
Relative dose intensity (%)
Median (range)
Data source: Statistical Output, Section

\* From Day 1 until last treatment intake + 30 days; Intended dose = nb of planned courses \* planned dose by course

Table ii-2 Dose reductions, delays and interruptions, AL / OHM safety population

```
N patients with \geq 1 dose
reduction
N reductions/patient
   1
   2
N patients with \geq 1 dose
interruption
N interruptions/patient
   1
   2
N patients with \geq 1 dose delay
N delay/patient
   1
N patients with \geq 1 dose increase
Data source: Statistical Output, Section
Listing ii-1 Reason for reduction/intracycle interruption/delay, AL / OHM enrolled patients
       Cabout
                           Dationt #
                                           Dece level / achedule Dec
                                                                         for noductio
                                                                                               Oth
```

Cohort	Patient #	Dose level / schedule Reason for reduction	Other
(AL/ OHM)		(initial)	

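### SAP 12.2 reports study duration in days, but its only formula is on a week scale with a whole week added; both dose-intensity denominators also lack a definition

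*SAP*

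**What the plan says.** SAP 12.2 lists the exposure variables as "study duration (days), treatment duration (days), number cycles initiated", followed by cumulative dose and the two dose intensities. Table ii-1 in the SAP appendix labels the same row as running from treatment "start to last dose last cycle", in days, with a median and range per patient and a total.

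The formula in 12.2 takes the last cycle dose date and the "first cycle dose date)/7 + 1". The minus sign between the two dates is missing from the extracted text. I assume the PDF reading lost it and do not count that as an error.

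The dose intensities follow: "Absolute dose intensity (mg/week) = Actual cumulative dose / Actual duration", with relative dose intensity as "Actual dose intensity / Planned dose intensity" in percent. Neither document defines the actual duration or the planned dose intensity. The nearest text is the last item of the same list, which gives the planned administration period as 21 days. It follows the line on cycle 1 cumulative dose and is not linked to either intensity. The treatment modifications include "delay (definition), or dose increase", where the bracket was evidently meant to hold a definition.

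Protocol 5.2.3 sets the cycle length: "one cycle = 21 days by convention and day 22 = day 1 of next cycle".

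**The concern.** A quantity labelled in days comes from a formula that divides by seven, so label and number cannot both be right. The position of the added 1 makes it worse. An inclusive count adds one day before any division; here the 1 is added after it and becomes a whole week. The output is therefore neither days nor correct weeks.

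If programmed as written, the study-duration row of Table ii-1 is wrong in every dose-level column and in the total. The undefined denominators raise a second question: a reader of the report could not tell what a given dose intensity means. The programmer would have to choose between the study duration, the separately listed treatment duration and whole cycles. On a schedule with a rest period these give different answers for the same patient.

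**Working it through.** **Inputs**
- Unit: days (SAP 12.2 and Table ii-1).
- Formula: D/7 + 1, where D is the last dose date minus the first dose date (SAP 12.2, minus sign assumed).
- Display: one decimal unless otherwise specified (SAP 6.1).
- Cycle: 21 days (Protocol 5.2.3; SAP synopsis).

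The documents give no numerical result from this formula, so there is no stated figure to reproduce.

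**Step 1. The formula as printed.** Inclusive days are D + 1, and inclusive weeks are (D + 1)/7.

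| Dosing span | D | D/7 + 1 | Displayed | Inclusive days | Inclusive weeks |
|---|---|---|---|---|---|
| Days 1–14 | 13 | 2.857 | 2.9 | 14 | 2.00 |
| Days 1–21 | 20 | 3.857 | 3.9 | 21 | 3.00 |
| Days 1–35 (two 14/21 cycles) | 34 | 5.857 | 5.9 | 35 | 5.00 |
| Days 1–84 | 83 | 12.857 | 12.9 | 84 | 12.00 |

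The excess over inclusive weeks is (D/7 + 1) − (D + 1)/7 = 6/7 = 0.857 week, the same for every patient.

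**Step 2. Another reading of the dates.** Suppose the cycle dose date means Day 1 of the cycle. One cycle gives 0/7 + 1 = 1.0, and two give 21/7 + 1 = 4.0. Neither is in days.

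**Step 3. Does the missing definition of dose intensity matter?** This is an illustration, not a prediction of what the tables will show. Take a fully adherent patient with one cycle at 80 mg once daily on 14 days of 21. The cumulative dose is 14 × 80 = 1120 mg. Assume planned intensity is the planned cycle dose per 21 days: 1120/3 = 373.3 mg/week.

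| Actual duration taken as | Weeks | Absolute intensity (mg/week) | Relative intensity |
|---|---|---|---|
| Printed formula, 13/7 + 1 | 2.857 | 392.0 | 105.0% |
| Unit corrected only, 14/7 | 2.00 | 560.0 | 150% |
| Full 21-day cycle | 3.00 | 373.3 | 100% |

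The dose cancels, so the percentages are 3/2.857, 3/2 and 3/3 at any dose. The 150% arises because the seven rest days count in the planned intensity but not in the actual one. If both use the 14-day span, planned intensity is 1120/2 = 560 mg/week and the patient scores 560/560 = 100%. Consistency between the two denominators is therefore what matters.

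**The case against.** The strongest reply is that the harm is conditional. The row label in Table ii-1 already states the intended quantity, SAP 5 has the programs validated by the statistician, and SAP 16.1 says the templates went through two dry runs validated by the sponsor. A programmer would probably notice. That limits the likely damage. It does not supply a correct formula, and SAP 6.1 makes this document the basis of the analysis. The second-statistician check in SAP 5 covers only the DLT criterion.

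A second reply is that planned intensity can be inferred from the planned dose per course and the 21-day administration period. That is a reasonable guess, and it is the one used in Step 3. It leaves the actual duration open, and the SAP does not tie the 21 days to either intensity.

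Three stronger readings are tempting and are not supported:
- **That reported relative dose intensity will be biased by schedule.** This requires the printed study duration to be the actual duration and planned intensity to be per 21 days. The SAP states neither, and other definitions give 100%.
- **That each dose-level column holds a single schedule, so any distortion can be read off by column.** The columns in SAP 6.1 show assigned schedules. The SAP synopsis lets ongoing acute leukemia patients be offered a move from the intermittent to the continuous schedule.
- **That the added 1 in the compliance formula of SAP 10.5 is the same error.** That depends on what one CRF line represents, and the documents do not show the CRF layout.

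**Conclusion.** The study-duration formula is wrong as written. It yields 3.857 (displayed 3.9) where the table calls for 21 days, and it overstates inclusive weeks by 6/7 week for every patient. This rests only on the lost minus sign and holds under both readings of the dates. The missing definitions of actual duration, planned dose intensity and delay are gaps of specification. The 100%, 105.0% and 150% show that the choice has consequences; they are not errors attributed to the plan.

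A reader might infer that the dose-finding conclusions are touched. They are not. DLT evaluability has its own 85% rule (SAP 8), and the recommended dose is set through DLTs and the committee's decisions. The effect is confined to descriptive exposure tables. The correction should be made before those tables are relied on, but it is modest in scope.

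**What to change.** 1. Replace the formula with: study duration (days) = last dose date − first dose date + 1. Where weeks are needed, use (last dose date − first dose date + 1)/7.
2. Define actual duration and planned dose intensity explicitly, in weeks, over the same span, with rest days treated alike in both. Correcting the unit alone is not enough, as the 150% shows. If the 21-day administration period is meant as the planned basis, say so in the dose-intensity formulas.
3. Complete the empty definition of a delay.

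The cost is one corrected formula, two definitions and one completed placeholder in the SAP and programs, then a rerun of the exposure tables. The duration correction needs no new data, since Protocol 5.2.3 requires "Details of the exact dose and time of administration of medication" to be documented, dated, and reported in the case report form. For patients who changed schedule, the definition of planned intensity should state which schedule applies. Protocol 5.4 records the allocated schedule on the registration form; the sponsor should confirm how later changes were captured.

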# **12.3 PRIMARY CRITERION: DOSE LIMITING TOXICITY**

DLTs are defined as any treatment-emergent adverse events (TEAEs) occurring during the first cycle (i.e., the first 21 days following study treatment initiation; note that hypocellular bone marrow and no marrow blasts in AL patients had to be confirmed at day 43), leading to treatment interruption or dose adjustment, or any unforeseen drug-related AE leading to study treatment interruption or discontinuation, unless a relationship to study medication can be definitively ruled out.

The number of patients evaluable for DLT/with DLT in cycle 1 will be tabulated per dose level and overall for safety population.

Type of DLT will be tabulated for patients evaluable for DLT by DL and overall.

### Non-hematologic DLTs

- Any grade 3 or 4 non-hematologic event (regardless of duration), unless it was not optimally treated with supportive care (e.g. grade 3 vomiting not adequately treated according to antiemetic standard of care).
- Grade 3-4 asymptomatic laboratory abnormal values lasting > 7 days. This definition applies for patients with lab values grade < 1 at baseline. For patients with grade 2 values (liver function test (LFTs) or creatinine clearance) at baseline, only grade 4 lasting > 7 days will be accounted as DLT, unless the SMC considers the event clinically significant.
- Any other AE (such as prolonged and intolerable grade 2 event) resulting in study drug discontinuation or interruption with or without dose reduction

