3.2.1 Non-hematological DLTs

- Any grade 3 or 4 non-hematological event (regardless of duration), unless it was not optimally treated with supportive care (e.g. grade 3 vomiting not adequately treated according to antiemetic standard of care).
- Grade 3-4 asymptomatic laboratory abnormal values lasting > 7 days. This definition applies for patients with lab values grade ≤ 1 at baseline. For patients with grade 2 values at baseline, only grade 4 lasting > 7 days will be considered DLT, unless the SMC considers the event clinically significant. See below for liver function tests*.
- Any prolonged grade 2 toxicity (lasting more than 2 weeks) leading to treatment interruption and/or dose reduction

* Any of the following liver test abnormalities** (see Appendix 16.12)

- ALT or $AST > 8 \times ULN$
- ALT or AST $> 5 \times ULN$ for > 2 weeks
- ALT or AST > 3 x ULN AND (total bilirubin > 2 x ULN OR INR > 1.5)
- ALT or AST > 3 x ULN with the appearance of fatigue, nausea, vomiting, right upper quadrant pain or tenderness, fever, rash and/or eosinophilia (> 5%), unless the investigator assesses the rash or fatigue to be related to OTX015 and not related to liver impairment with sponsor's agreement.

**Note: All patients with these liver test abnormalities should be monitored weekly until all abnormalities return to normal or to the baseline state. For patients with isolated total bilirubin increases >2 x ULN or 2 x baseline (if elevated at baseline), except if associated with direct bilirubin \leq ULN, monitoring should be every 2 weeks until bilirubin returns to normal or to the baseline state. Drug induced liver injury (DILI) may develop or progress even after the causative

drug has been stopped. Results should be recorded on the CRF and in the database. See guidelines on the handling of these events (potential Hy's law cases).

Investigators must be warned about qualifying fatigue/asthenia as a DLT. Grade 3 fatigue/asthenia deemed to be related to the study medication is a DLT as per protocol. However, multiple causal events, often intricate, may result in severe fatigue/asthenia in cancer patients participating to a phase I clinical trial, including disease progression, concomitant medications, concomitant medical conditions, anxiety, depression, transportation, etc.

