5.3 TREATMENT DURATION

Treatment will be continued until:

- Disease progression
- Intolerable toxicity
- Treatment interruption for > 2 weeks due to toxicity (except in case of suspicion hematological DLT in acute leukemia, where treatment interruption for 3 weeks is allowed to confirm DLT)
- Recurrence of DLT despite dose reduction.
- Any of the following liver test abnormalities (see Appendix 16.12)
 - ALT or $AST > 8 \times ULN$
 - ALT or AST $> 5 \times ULN$ for > 2 weeks
 - ALT or AST > 3 x ULN and (total bilirubin > 2 x ULN OR INR > 1.5)
 - ALT or AST > 3 x ULN with the appearance of fatigue, nausea, vomiting, right upper quadrant pain or tenderness, fever, rash and/or eosinophilia (> 5%), unless the investigator assesses the rash or fatigue to be related to OTX015 and not related to liver impairment with sponsor's agreement
- Patient's request (consent withdrawal).

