### Dose & schedule adaptation

Study product dosing (OTX015/MK-8628) will be interrupted in case of: Non-hematologic toxicities:

- any grade 3-4 non hematologic toxicity despite adequate medication, regardless of duration;
- grade 3-4 asymptomatic non hematologic laboratory abnormal values, deemed related to study medication, lasting > 7 days. This definition applies for patients with LFTs/creatinine clearance grade < 1 at baseline. For patients with grade 2 values at baseline, only grade 4 lasting > 7 days will be considered DLT, unless the SMC considers the event clinically significant.
- Any prolonged grade 2 toxicity (lasting more than 2 weeks), leading to treatment interruption and/or dose reduction.

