# 6. STATISTICAL METHODOLOGY

# 6.1 GENERAL CONSIDERATIONS

The statistical analysis will be performed by eXYSTAT, under the responsibility of the Sponsor OncoEthix GmbH and the study CRO, OTD, on the basis of the present document.

The statistical analysis will be performed using SAS® software, version 9.4 in a Windows XP operating system environment.

The baseline value is defined as the last available value prior to administration of the investigational product.

The study treatment phase is defined as the period between the date of first administration of investigational product and the date of last administration of investigational product + 30 days.

No replacement of missing values is planned, other than those noted in Section 6.2. Thus the number of patients included in the analyses may vary depending on availability of the parameter considered.

Descriptive statistics will be provided by dose level (DL1 to DL5 or DL6 then expansion cohort, depending on the disease cohort) and overall for each of the two patient cohorts (AL and OHM), and by time point when appropriate, according to the nature of the variable.

- For quantitative variables, descriptive statistics will include: number of missing values, number of observed values, minimum, maximum and median or mean and standard deviation.

- For qualitative variables, descriptive statistics will include: number and percentage of missing values, number of observed values, frequencies and percentages (only for the overall column) per modality.

Calculated statistics and percentages will be displayed with one decimal, unless otherwise specified.

No statistical tests will be performed due to the descriptive nature of this analysis.

In terms of terminology, the mention of "by dose level and overall" will always correspond to the following, according to the cohort:

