# 8. POPULATIONS

Enrolled Population: all patients who signed an Informed Consent Form.

Treated/Safety Population: all included patients receiving at least one dose of the investigational drug.

**Evaluable for Efficacy Population:** All treated patients with at least one available tumor assessment (BM aspiration for AL patients or imaging for OHM patients) by the end of cycle 2 or later, OR with earlier evidence (i.e. cycle 1) of response or progression.

**Evaluable for DLT Population:** all treated patients receiving at least 85% of the intended OTX015/MK-8628 dose during the first cycle (i.e.  $\geq$  12 days at full dose for AL and  $\geq$  18 days at full dose for other hematologic malignancies)\*, as well as patients not fulfilling these conditions, but who experienced DLT.

\*e.g. for DL1 (10 mg/day), AL patients receiving  $\geq$  120 mg over the first 21 days (10 mg x 12), or other hematologic malignancy patients receiving  $\geq$  180 mg over the first 21 days (10 mg x 18).

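### SAP 12.3 drops the protocol's liver DLT list and puts LFTs under a narrower laboratory rule, so for patients with grade 2 LFTs at baseline the primary endpoint conflicts with the protocol and within the SAP

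*SAP*

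**What the plan says.** **Protocol.** Section 3.2.1 counts asymptomatic grade 3-4 laboratory values that last more than 7 days. For a grade 2 baseline value it asks for grade 4 lasting more than 7 days, unless the SMC finds the event clinically significant. It then adds "See below for liver function tests" and lists four liver abnormalities:

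- ALT/AST above 8x ULN
- ALT/AST above 5x ULN for more than 2 weeks
- "ALT or AST > 3 x ULN AND (total bilirubin > 2 x ULN OR INR > 1.5" (third item)
- ALT/AST above 3x ULN with specified symptoms or eosinophilia

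None of the four has a baseline-grade or grade 4 condition, and only the second has a duration. The lead of section 3.2 adds that the event must lead to dose modification, interruption or discontinuation. The protocol synopsis also names liver test abnormalities in its DLT definition. Section 5.3, under "Any of the following liver test abnormalities (see Appendix 16.12", makes the same four items reasons to end treatment.

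**SAP.** The second non-hematologic bullet of 12.3 says that, given "grade 2 values (liver function test (LFTs) or creatinine clearance) at baseline, only grade 4 lasting > 7 days will be accounted as DLT", and then gives the same SMC exception. There is no liver list and no pointer. The SAP synopsis also places LFTs in the laboratory rule ("This definition applies for patients with LFTs/creatinine clearance grade < 1 at baseline"), and its DLT definition has lost the reference to liver tests. The third bullet of 12.3 counts "Any other AE (such as prolonged and intolerable grade 2 event) resulting in study drug discontinuation or interruption with or without dose reduction". SAP 14 declares three changes: no per-protocol analysis, no overall survival analysis, and no PK/PD relationship analyses. None concerns DLT.

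**The concern.** DLT is the primary endpoint, and SAP 5 has a second statistician validate it, so its definition should give one answer for each event. Here a statistician working from protocol 3.2.1 and another working from SAP 12.3 could classify the same liver event differently. The table of DLTs could then disagree with the protocol and with the DLTs that the SMC validated under protocol Appendix VIII.

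The classification also reaches the denominator. SAP 8 defines the DLT-evaluable population as patients with at least 85% of the intended cycle 1 dose, "as well as patients not fulfilling these conditions, but who experienced DLT". Whether a patient stopped early for a liver event is evaluable depends on whether that event is called a DLT. The liver is the main target organ in the nonclinical studies (protocol 1.1.2.5), so this part of the definition is not incidental.

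**Working it through.** There is no figure in the plan to reproduce, so the check sets the rules side by side and runs cases through them.

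**Setting.** Patient with grade 2 LFTs at baseline; asymptomatic event in cycle 1; relationship to drug not ruled out; dosing changed as a result.

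**Rules.**

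- Protocol list: DLT if ALT/AST > 8x ULN; or > 5x ULN for > 14 days; or > 3x ULN with bilirubin > 2x ULN or INR > 1.5.
- SAP bullet 2: DLT only if grade 4 and > 7 days, or if the SMC judges the event significant.
- SAP lead sentence and bullet 3: can count an AE that led to interruption or discontinuation.

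**Assumption.** CTCAE cut-offs are not in the documents. I take ALT grade 3 as > 5x to 20x ULN and grade 4 as > 20x ULN, and treat bilirubin at 2.5x ULN as below grade 4.

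| Event | Protocol list | SAP bullet 2, before SMC judgement | SAP lead sentence or bullet 3, drug stopped |
|---|---|---|---|
| ALT 9x, 5 days | DLT | Not DLT (5 days is not > 7) | Could count |
| ALT 9x, 10 days | DLT | Not DLT (below grade 4) | Could count |
| ALT 6x, 15 days | DLT | Not DLT (below grade 4) | Could count |
| ALT 4.5x with bilirubin 2.5x, 10 days | DLT | Not DLT (below grade 4) | Could count |
| ALT 25x, 5 days | DLT | Not DLT (5 days is not > 7) | Could count |
| ALT 25x, 8 days | DLT | DLT | Could count |

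The first and fifth rows do not depend on the cut-offs, because the duration condition alone fails. The rows are chosen to show how the rules behave; they say nothing about frequency.

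**Reading the last two columns together.** Bullet 2 is specific to LFTs and says only; bullet 3 is general and speaks of any other AE. The SAP does not say which prevails. Bullet 1, on grade 3-4 events of any duration, reads the same in both documents and does not settle the matter. Bullet 3 does not mention a dose reduction without interruption, although the lead sentence mentions dose adjustment. The fourth protocol item, ALT/AST > 3x ULN with symptoms, lies outside a rule for asymptomatic values and is not part of the conflict.

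**Can such a patient be enrolled?** Yes, within limits. Protocol 4.2 and the SAP synopsis both allow ALAT/ASAT up to 5x UNL with liver involvement; the protocol synopsis gives 3x without that exception. Both parts of the protocol allow bilirubin up to 2x UNL with liver involvement.

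**Timing.** The protocol is Version J of 18 December 2015; the SAP refers to dry runs in December 2016 and February 2017, so it is the later document. The documents do not say when the liver list entered the protocol. If it was there from the start, it covers all 80 + 61 = 141 patients. If it came only with Version J, it covers about the last 14 days (to 1 January 2016) to 44 days (to 31 January 2016) of an enrolment planned from January 2013 to January 2016.

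**The case against.** The strongest reply is that the SAP still catches these events. A liver event on the list normally ends treatment under protocol 5.3. Under protocol 7.3.2.2 a laboratory change with that consequence must be reported as a TEAE, so it falls under the SAP lead sentence and bullet 3. The SMC exception follows directly after the bullet 2 wording, and suspected DLTs were captured prospectively on the SAE form. This stands in part. A reader might infer that the SAP removes these DLTs outright, and the text does not support that. What remains is that a DLT by rule in the protocol becomes a non-DLT by default under the one SAP bullet that names LFTs, with recovery left to a general bullet or to SMC judgement.

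A reader might also infer that a patient stopped early would vanish from both numerator and denominator at a dose level. Protocol 3.1.1 and section 9 replace non-evaluable patients, and an event that the SMC counted would ordinarily meet the SMC clause as well. Nor would the event be hidden. It would be missing from Listing i-1 if not called a DLT, but could be expected among the patients not evaluable for DLT (Listing i-2 under patient disposition) if under 85% of dose, and in the listings of AEs leading to discontinuation if drug was stopped.

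Eligibility makes the group small, but does not empty it. Finally, the SAP synopsis also lacks the INR/aPTT and haemoglobin entry criteria of the protocol synopsis, which suggests carried-over text more than a decision to narrow the endpoint. That may well be so. It explains the difference but does not resolve it.

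**Conclusion.** The point holds as an inconsistency in the definition of the primary endpoint that should be corrected. For grade 2 LFTs at baseline, SAP 12.3 contradicts protocol 3.2.1 on asymptomatic ALT/AST above 8x ULN, above 5x ULN for more than 2 weeks, and above 3x ULN with raised bilirubin or INR. It also contradicts its own lead sentence and third bullet, and SAP 14 is silent. For lower baseline grades the SAP is unclear, but there is no direct conflict.

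The size is unknown. It is likely small, since it needs a raised LFT at entry and a qualifying event in cycle 1, and it may be zero. Each case would change a dose-level DLT count by one. It would be tempting to conclude that the 80 mg recommended dose rests on an undercount. The documents give no DLT data that would show this, and dose decisions belonged to the SMC under the protocol. The contradiction does not depend on CTCAE cut-offs for events lasting 7 days or less; for longer events it rests on the cut-offs assumed above.

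**What to change.** Copy the four-item liver list of protocol 3.2.1 into SAP 12.3 and state that it governs LFTs in place of the asymptomatic-laboratory bullet. If the list applied only from a later protocol version, say so in SAP 14 and state which rule applied to which patients.

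In Listing i-1, include and flag any cycle 1 liver event that is a DLT under only one of the two rules. If any exist, report the DLT count and the DLT-evaluable N both ways; if none exist, one sentence saying so is enough.

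The cost is a paragraph or an entry of text, one flag, and a short derivation. Listing vi-3 gives baseline grade, worst grade and absolute values, but not the ULN multiple, duration or concurrent bilirubin and INR. These have to be derived from the individual laboratory listings of SAP 12.6. No new data are needed.
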